Treated Period Follow-Up. Patients will be followed over the period treated with advanced RCC therapy. Time treated will be defined as the time from the index date to the date of the end of the last advanced metastatic RCC prescription (end of supply for orals/administration date plus 30 days for injectables), end of enrollment, end of follow up, or death (see more specifics on oral versus injectable rules in [6.3.1 Variables](#) section of this protocol).

Analysis 2. Describe various treated populations of interest by demographics, clinical characteristics, as well as cost and utilization

Describe the demographics and other baseline characteristics of the first-line treated cohorts of interest identified in the treatment patterns analysis (Analysis 1) for RCC patient as follows:

Baseline Characteristics (see [6.3.2 Baseline Characteristics](#)):

- Age at index;
- Gender;
- Race;
- Region;

PFIZER CONFIDENTIAL

- Payor;
- Clinical characteristics: Quan-Charlson Comorbidity Index (CCI) scores and baseline comorbidities;
- Prior treatment (6 months prior) - nephrectomy, radiation/ablation, interferon, high-dose interleukin-2, other anti-neoplastic medications;
- Secondary malignancy locations (6 months prior);
- Baseline costs of care (6 months prior);
- Baseline health care resource utilization (6 months prior).

Analysis 3: Evaluate the key outcomes of interest for advanced RCC therapy regimens toward demonstrating existing unmet needs in RCC given currently available therapies (eg, ipilimumab/nivolumab).

Treatment duration, discontinuation, interruption, switching and therapy augmentation will be presented, as will the burden of disease costs and health care utilization. Survival will also be explored, although regimens are too new for extensive follow-up time.

Overall Outcomes Study Period. For the outcomes analysis, follow-up will be defined as the time from the index date to the end of specified follow up period of 6 months, end of enrollment, or death. Follow-up may vary given sample sizes of study population, with by subanalysis using 1-year or 2-years of follow-up time from study index date for certain sub-populations.

Outcomes include:

- **Time to Treatment Failure (TTF)** – First line time to treatment failure (TTF) is defined as the time from first-line therapy start to treatment discontinuation for any reason, including switched, augmented therapy, end of enrollment, death.

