6.3.2. Baseline Variables

Table 6. Baseline Variables

[figure not shown]
Variable	Operational definition
Baseline demographics	
Index Date	Date of first RCC diagnosis on record
Index Year	Index year for the patient
Age	Continuous: Years Patient age at index date
Sex	Categorical: Male or female
Insurance Coverage	Categorical: Commercial, Medicare, or Medicaid
US Region	Categorical: Northeast, Midwest, South, West
Race	Categorical: based on each database
Clinical characteristics	
Time to systemic therapy <1 year	From IMDC: <1 year from time of diagnosis to systemic therapy
NCI Charlson comorbidity index (DCI)	Categorical: 0, 1-2, 3+
History of smoking	Categorical: Yes/No Prior history of smoking – record of smoking cessation medication or V code.
History of systemic therapy	Categorical: Yes/No A record of being given certain systemic drugs (interferon, interleukin 2, gemcitabine and doxorubicin)
History of surgical resection	Categorical: Yes/No History of nephron sparing or radical nephrectomy. ICD-10-CM Z90.5/ICD-9-CM V45.73 Acquired absence of kidney.

PFIZER CONFIDENTIAL

Variable	Operational definition
History of radiation therapy	
Categorical: Yes/No
 
ICD-10-CM Z51.0/ICD-9-CM V58.0 Encounter for radiotherapy.
 
ICD-10-PCS › D › Urinary System:
 
• DT0 Beam Radiation;• DT1 Brachytherapy;• DT2 Stereotactic Radiosurgery;• DTY Other Radiation. 
CPT Codes:
 
77401 Radiation treatment delivery, superficial and/or ortho voltage, per day;
 
77402 Radiation treatment delivery, >1MeV; simple;
 
77407 intermediate;
 
77412 complex.
 
New Codes
 
77085 Dual-energy x-ray absorptiometry (DXA), bone density study, 1 or more sites; axial skeleton (eg, hips, pelvis, spine), including vertebral fracture assessment.
 
77086 Vertebral fracture assessment via dual energy X-ray absorptiometry (DXA).
 
77306 Teletherapy isodose plan; simple (1 or 2 unmodified ports directed to a single area of interest), includes basic dosimetry calculation(s).

PFIZER CONFIDENTIAL

[figure not shown]

Variable	Operational definition

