	
77307 complex (multiple treatment areas, tangential ports, the use of wedges, blocking, rotational beam, or special beam considerations), includes basic dosimetry calculation(s).
 
77316 Brachytherapy isodose plan; simple (calculation[s] made from 1 to 4 sources, or remote afterloading brachytherapy, 1 channel), includes basic dosimetry calculation(s).
 
77317 intermediate (calculation[s] made from 5 to 10 sources, or remote afterloading brachytherapy, 2-12 channels), includes basic dosimetry calculation(s).
 
77318 Intensity modulated radiation treatment delivery (IMRT), includes guidance and tracking, when performed; simple.
 
77385 Intensity modulated radiation treatment delivery (IMRT), includes guidance and tracking, when performed; simple.
 
77386 complex.
 
77387 Guidance for localization of target volume for delivery of radiation treatment delivery, includes intrafraction tracking, when performed.
 
Deleted Codes (may be in the historic data, though no longer in use)
 
72291 Radiological supervision and interpretation, percutaneous vertebroplasty, vertebral augmentation, or sacral augmentation (sacroplasty), including cavity creation, per vertebral body or sacrum; under fluoroscopic guidance.
 
72292 under CT guidance.
 
74291 Cholecystography, oral contrast; additional or repeat examination or multiple day examination.
 
76645 Ultrasound, breast(s) (unilateral or bilateral), real time with image documentation.
 
76950 Ultrasonic guidance for placement of radiation therapy fields.
 
77080 Dual-energy X-ray absorptiometry (DXA), bone density study, 1 or more sites; axial skeleton (eg, hips, pelvis, spine).
 
77305 Teletherapy, isodose plan (whether hand or computer calculated); simple (1 or 2 parallel opposed unmodified ports directed to a single area of interest).
 
77310 intermediate (3 or more treatment ports directed to a single area of interest).

PFIZER CONFIDENTIAL

Variable	Operational definition

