	
77315 complex (mantle or inverted Y, tangential ports, the use of wedges, compensators, complex blocking, rotational beam, or special beam considerations).
 
77326 Brachytherapy isodose plan; simple (calculation made from single plane, 1 to 4 sources/ribbon application, remote afterloading brachytherapy, 1 to 8 sources).
 
77327 intermediate (multiplane dosage calculations, application involving 5 to 10 sources/ribbons, remote afterloading brachytherapy, 9 to 12 sources).
 
77328 complex (multiplane isodose plan, volume implant calculations, over 10 sources/ribbons used, special spatial reconstruction, remote afterloading brachytherapy, over 12 sources).
 
77403 Radiation treatment delivery, single treatment area, single port or parallel opposed ports, simple blocks or no blocks; 6-10 MeV.
 
77404 11-19 MeV.
 
77406 20 MeV or greater.
 
77408 Radiation treatment delivery, 2 separate treatment areas, 3 or more ports on a single treatment area, use of multiple blocks; 6-10 MeV.
 
77409 11-19 MeV.
 
77411 20 MeV or greater.
 
77413 Radiation treatment delivery, 3 or more separate treatment areas, custom blocking, tangential ports, wedges, rotational beam, compensators, electron beam; 6-10 MeV.
 
77414 11-19 MeV.
 
77416 20 MeV or greater.
 
77418 Intensity modulated treatment delivery, single or multiple fields/arcs, via narrow spatially and temporally modulated beams, binary, dynamic MLC, per treatment session.
 
77421 Stereoscopic X-ray guidance for localization of target volume for the delivery of radiation therapy.

PFIZER CONFIDENTIAL

Variable	Operational definition
Location of metastasis	
Categorical: by location (% of patients for each):
 

 Lymph nodes (ICD9-196.xx, ICD10 – C77)
 Lung (ICD9-197.0x, ICD10-C78.00)
 Liver (ICD9-197.7x, ICD10-C78.7)
 Brain (ICD9-198.3x, ICD10-C79.31)
 Bones (ICD9-198.5x, ICD10-79.5x)
 Adrenal gland (ICD9-198.7x, ICD10-79.7)
 Other (ICD9 196.xx-199.xx and ICD10 C77-C80 exclusive of above categories)

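### History of radiation therapy (Table 6) misses non-urinary treatment coded only in ICD-10-PCS and stereotactic treatment that carries no other listed code

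*Combined protocol and SAP*

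**What the plan says.** Table 6 in Section 6.3.2 builds History of radiation therapy from three components:

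- A diagnosis code for the encounter, "ICD-10-CM Z51.0/ICD-9-CM V58.0 Encounter for radiotherapy".
- ICD-10-PCS procedure codes under the single heading "ICD-10-PCS › D › Urinary System": DT0 (beam), DT1 (brachytherapy), DT2 (stereotactic) and DTY (other). The stereotactic entry reads "DT2 Stereotactic Radiosurgery".
- A list of CPT codes, in current, new and deleted groups. It includes conventional delivery, for example "77402 Radiation treatment delivery, >1MeV; simple", and intensity-modulated delivery, for example "77385 Intensity modulated radiation treatment delivery (IMRT), includes guidance and tracking, when performed; simple". The rest are isodose planning, image guidance and some entries unrelated to radiotherapy.

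Section 6.1, Analysis 2, gives the purpose. Prior treatment over the 6 months before index is to be described as "nephrectomy, radiation/ablation, interferon, high-dose interleukin-2, other anti-neoplastic medications", with no anatomical limit on the radiation. Section 6.2.1 requires at least two secondary malignancy codes and excludes the secondary kidney codes from those that qualify. Table 6 then names nodes, lung, liver, brain, bones and adrenal gland as metastatic locations, plus an Other category. Section 6.7 plans descriptive statistics and a standardized difference for each variable.

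**The concern.** The population is metastatic by construction, and none of the six named metastatic sites belongs to the urinary system. A procedure-code component confined to that system cannot register treatment of those sites. Listing DT2 shows that the authors meant stereotactic treatment to count, yet the CPT component offers no counterpart to it. A patient irradiated at a metastatic site can therefore enter the analysis as never irradiated.

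At stake is the reported frequency of prior radiation in each first-line cohort (Objective 2), and the standardized difference used to compare cohorts on it. Section 6.9 also mentions multivariate analysis or propensity score matching as possible ways to handle confounding. If such an analysis were added, this variable would be a natural covariate and would carry its misclassification with it.

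**Working it through.** The plan states no figure to reproduce. The check is a reading of the whole code list, followed by an illustration of why no size can be given.

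**Step 1. ICD-10-PCS coverage.** There are four entries, all under the urinary heading. Body systems covered: 1. Codes for any other body system: 0.

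**Step 2. CPT coverage, sorted by printed descriptor.**

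| Type | Codes | Count |
|---|---|---|
| Conventional or intensity-modulated delivery | 77401, 77402, 77407, 77412; 77318 (as labelled), 77385, 77386; 77403, 77404, 77406, 77408, 77409, 77411, 77413, 77414, 77416, 77418 | 17 |
| Isodose planning | 77306, 77307, 77316, 77317; 77305, 77310, 77315, 77326, 77327, 77328 | 10 |
| Guidance | 77387; 76950, 77421 | 3 |
| Not radiotherapy | 77085, 77086; 72291, 72292, 74291, 76645, 77080 | 7 |
| Stereotactic delivery | none | 0 |

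Total: 17 + 10 + 3 + 7 = 37. Code 77318 carries the same intensity-modulated descriptor as 77385, although it follows two brachytherapy planning codes. If it were moved to planning, the split would be 16 and 11, and the stereotactic count would still be 0. The nearest entry in wording, "77421 Stereoscopic X-ray guidance for localization of target volume for the delivery of radiation therapy", is imaging guidance, not delivery. Ten of the 17 delivery codes stand in the deleted group, which the plan describes as possibly present in historic data but no longer in use.

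**Step 3. What still gives Yes.** The plan does not state how the codes combine. I read the item as Yes if any listed code is present. On that reading, Z51.0/V58.0 and the delivery, planning and guidance codes are not restricted to the urinary system, so each can turn the item to Yes for treatment at a metastatic site.

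**Step 4. What gives No despite irradiation.** Two routes remain:

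- Treatment at a non-urinary site recorded only by an ICD-10-PCS procedure code.
- Stereotactic treatment with no other listed code on the patient's record.

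**Step 5. Size.** Let s be the share of irradiated patients treated only by an uncovered route, and q the chance that some other listed code catches them. Sensitivity is then 1 − s(1 − q). The documents give neither input. With assumed ranges s = 10% to 50% and q = 0 to 0.9:

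- Lowest: 1 − 0.50 × (1 − 0) = 0.50.
- Highest: 1 − 0.10 × (1 − 0.9) = 0.99.

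If true prevalence were 30% (also assumed), these would be seen as 0.30 × 0.50 = 15% and 0.30 × 0.99 = 29.7%. The range is too wide to serve as an estimate.

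**Step 6. Direction.** The seven non-radiotherapy codes create false Yes records. If f is the false-Yes rate among unirradiated patients and p the true prevalence, the net error is −p(1 − sensitivity) + (1 − p)f. With p = 30%, s = 0.3 and q = 0.5, sensitivity is 1 − 0.3 × 0.5 = 0.85 and the loss is 0.30 × 0.15 = 4.5 percentage points. A false-Yes rate of 0.045 / 0.70 = 6.4% would cancel it, and a higher rate would reverse the sign. These inputs are assumptions too. They show only that the sign cannot be fixed from the documents.

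**The case against.** The strongest reply is that the definition has several components that do not depend on site. A patient given conventional or intensity-modulated treatment to brain, bone or lung is caught by the delivery codes, and Z51.0/V58.0 catches any modality when it is recorded. Even a stereotactic course may leave a listed planning or guidance code, such as 77307 or 77387. This stands, and it narrows the point to the two routes in Step 4 of the working. A reader might infer from the urinary heading that radiotherapy to metastases is missed in general; the list does not support that.

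A reader might also try to attach a percentage. Taking 20–40% of irradiated patients as stereotactic-only and 30–70% of those as carrying Z51.0 gives 0.20 × 0.30 = 6% to 0.40 × 0.70 = 28% missed. Both inputs are unsupported by the documents, and the calculation treats Z51.0 as the only rescue when planning and guidance codes also give Yes.

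A third inference is that cohorts with more brain or bone metastases will look less pre-treated than they are. The documents do not show that the missed cases concentrate there. Several of the unrelated codes concern bone density, vertebral fracture or vertebroplasty, and could push patients with bone disease the other way.

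Finally, the impact is small. In the visible text, radiation history plays no part in eligibility, regimen assignment or any outcome. That is correct and sets the weight of the point, but it does not make the code list right.

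**Conclusion.** The gap is real and can be seen on the face of Table 6: one ICD-10-PCS body system out of those available, and no CPT descriptor for stereotactic delivery, in a population required to have metastatic disease and for an item described elsewhere without a site limit. Some irradiated patients can be recorded as No.

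The size of the under-count and its net direction between cohorts cannot be estimated from the documents. The consequence is limited to the reported frequency of one descriptive baseline variable and its standardized differences, so this is a minor point. The conclusion assumes that any single listed code gives Yes and that no fuller code list exists outside the protocol. On the second assumption, Section 6.7 says that no separate SAP is required, and Annex 1 lists no stand-alone documents.

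**What to change.** Revise the Table 6 entry once, covering both kinds of error:

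- Extend the four ICD-10-PCS section D modalities (beam, brachytherapy, stereotactic, other) from the urinary system to all body systems.
- Add the CPT codes for stereotactic delivery. The protocol does not list these, so they should be taken from the CPT code books for the years that the baseline period covers.
- In the same revision, remove the seven codes that are not radiotherapy (77080, 77085, 77086, 72291, 72292, 74291, 76645) and check the descriptor printed for 77318.
- State that any one listed code gives Yes.

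If the list is not extended, the variable should be relabelled to say what it covers. Reporting how many patients become Yes only through the added codes would give the size that the documents cannot.

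The cost is a code-list edit and a small amount of reprogramming, repeated in each database. No eligibility rule or outcome changes.

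### Seven of the 37 CPT codes that define radiation history in Table 6 are not radiotherapy by their own descriptions, so the flag can be set to Yes in patients who were never irradiated

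*Combined protocol and SAP*

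**What the plan says.** Table 6 in Section 6.3.2 gives "History of radiation therapy" as a Yes/No variable, followed by ICD-9 and ICD-10 codes and a CPT list in three parts: an opening group, a group of new codes, and a group of deleted codes retained because they may still occur in older claims.

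Two entries among the new codes are bone imaging:
- "77085 Dual-energy x-ray absorptiometry (DXA), bone density study, 1 or more sites; axial skeleton"
- "77086 Vertebral fracture assessment via dual energy X-ray absorptiometry (DXA"

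Five entries among the deleted codes are also not radiotherapy:
- "77080 Dual-energy X-ray absorptiometry (DXA), bone density study, 1 or more sites; axial skeleton"
- "74291 Cholecystography, oral contrast; additional or repeat examination or multiple day examination"
- "76645 Ultrasound, breast(s) (unilateral or bilateral), real time with image documentation"
- 72291, radiological supervision of vertebroplasty under fluoroscopy
- "72292 under CT guidance", the CT variant of 72291

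Section 6.1 (Analysis 2) lists prior radiation or ablation among the baseline characteristics of the first-line cohorts, with a look-back of 6 months. Section 6.7 plans standardized differences for each variable and says that no separate SAP is required. Annex 1 lists no stand-alone documents. Section 6.8 says that programming follows the protocol's specifications.

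**The concern.** A Yes/No variable followed by a list of codes is naturally programmed so that any one code on the list gives Yes. Nothing in Table 6 requires an accompanying radiation delivery code, and no other section takes the seven codes out. A patient whose only match is a bone density scan would then be recorded as having had radiotherapy.

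The protocol is the only specification, so no later document is planned that would catch this. The independent check in Section 6.8 works from the same specification, so it could confirm the faulty list. Replication across databases would repeat the error.

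At stake are the accuracy of one planned descriptor under Objective 2 and the standardized difference calculated from it. If the matching or multivariate methods mentioned in Section 6.9 were ever used, the misclassified variable could also enter those.

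**Working it through.** **Count of codes.** The inputs are the CPT codes printed in Table 6, sorted by their own descriptions.

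| Part of the list | CPT codes | Not radiotherapy by description |
|---|---|---|
| Opening group | 4 | 0 |
| New codes | 10 | 2 (77085, 77086) |
| Deleted codes | 23 | 5 (72291, 72292, 74291, 76645, 77080) |
| Total | 37 | 7 |

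7 / 37 = 18.9%. The remaining 37 − 7 = 30 codes are all described as radiation delivery, isodose planning, or guidance or localization for radiation. Code 76950 is ultrasound guidance for placing radiation fields and belongs with these 30. Two of the seven need a moment's reading. Code 72292 is a child line that continues the vertebroplasty description of 72291. Code 77086 is vertebral fracture assessment by DXA, which is only loosely bone densitometry but clearly not radiotherapy.

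**Period searched.** Section 6.2.1 puts index dates between April 2018 and 31 March 2019. Section 6.1 defines the index date as treatment initiation and gives a 6-month look-back. The earliest relevant claims are therefore from about October 2017. Table 6 states no look-back for this variable, and Section 6.4 mentions a data window of 24 months before index.

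**Effect on the reported share.** The documents give no frequencies for any of these codes and no expected prevalence of prior radiation, so there is no plan figure to reproduce. Let p be the true share irradiated and q the share of non-irradiated patients with at least one of the seven codes in the look-back. Both are assumptions.

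- Reported share = p + (1 − p) × q
- Share of flagged patients who are false positives = (1 − p) × q / reported share

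With p = 25%:

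| q | Reported share | False positives among flagged |
|---|---|---|
| 0% | 25.0% | 0% |
| 1% | 25 + 0.75 = 25.75% | 0.75 / 25.75 = 2.9% |
| 3% | 25 + 2.25 = 27.25% | 2.25 / 27.25 = 8.3% |
| 5% | 25 + 3.75 = 28.75% | 3.75 / 28.75 = 13.0% |
| 10% | 25 + 7.5 = 32.5% | 7.5 / 32.5 = 23.1% |

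The false-positive fraction depends on p. At q = 5% it is 31% when p = 10% (reported share 14.5%), and 10% when p = 30% (reported share 33.5%).

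**Effect on a standardized difference.** If q is the same in two cohorts, the difference in shares shrinks by the factor (1 − q). As an illustration, take true shares of 20% and 30%, q = 10%, and cohorts of equal size. The reported shares are 28% and 37%.

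- True: 0.10 / √((0.20 × 0.80 + 0.30 × 0.70) / 2) = 0.10 / 0.430 = 0.23
- Reported: 0.09 / √((0.28 × 0.72 + 0.37 × 0.63) / 2) = 0.09 / 0.466 = 0.19

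So a bias in the standardized difference does not require unequal q. Unequal q could move it in either direction.

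**The case against.** The strongest reply is that the problem may hardly show in the data. Five of the seven codes, including the breast ultrasound and both vertebroplasty codes, stand under a heading saying they are no longer in use. With claims starting around October 2017, they may appear rarely or never. This stands as far as it goes, although the documents give no deletion dates, so the contribution of the five is unknown rather than zero. It does not reach 77085 and 77086, which are listed as new codes.

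The any-code rule is also an inference, because Table 6 gives a list and never states how the flag is set. That is correct. It is still the plain reading, and no alternative rule is offered.

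The variable is one descriptive item. It is neither an eligibility criterion nor an outcome, no adjusted model is specified, and Section 6.9 says only that matching or multivariate methods can be used. This stands and limits the consequence.

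A reader might go further and infer that, because DXA and vertebroplasty relate to age, sex and bone disease, the false positives must fall unequally on the treatment cohorts. The documents do not support that. They give no frequency of these codes by regimen, age or sex, and Section 6.7 does not even name the groups that the standardized differences compare.

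**Conclusion.** The code list is wrong as written: seven of 37 CPT codes do not describe radiotherapy, and nothing in the protocol neutralizes them. If any listed code sets the flag, patients with one of these codes and no true radiotherapy code would be misclassified as irradiated.

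The size cannot be determined from the documents and may be small. Under an assumed true prevalence of 25% and q between 0% and 10%, the overstatement is 0 to 7.5 percentage points. The lower end is plausible if the deleted codes are absent from the look-back and the two current ones are uncommon. Differential error across cohorts is a possibility only. No primary outcome is affected. The point is a correction that should be made because the definition is invalid and easy to repair, not because a large bias has been shown.

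**What to change.** In Table 6, delete 77085, 77086, 77080, 72291, 72292, 74291 and 76645 from the radiation-history list. Keep the 30 codes for radiation delivery, planning and field guidance, including 76950, and leave the ICD codes unchanged. Add one sentence stating that any listed code within the look-back sets the flag to Yes, and state the look-back in the same row so that it agrees with Section 6.1.

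While the list is open, check 77318: it follows the brachytherapy planning codes but carries the same description as 77385. Both descriptions are radiotherapy, so this does not alter the flag.

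The cost is an edit to one row of one table and the matching code list in the program. No additional data are needed, and no code described as radiation is lost.

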6.2.1. Inclusion Criteria

Subjects will be selected irrespective of their survival status. Patients must meet all of the following inclusion criteria to be eligible for inclusion in the study:

- **Index date:** The first prescription or administration of one of the medications indicated for advanced RCC recorded in the database between April 2018-March 31, 2019, among those with no aRCC treatment in their history.
- Age 18 years or older in the year of the index first line therapy prescription.
- 2 or more RCC diagnoses (ICD-9: 189.0; ICD-10: C64.1, C64.2, C64.9) at least 30 days apart, in the 1 year prior to the index date until 30 days post index date.

PFIZER CONFIDENTIAL

- 2 or more code for secondary malignancy codes indicating possible diagnoses for metastatic disease at least 30 days apart, in the 1 year prior to the index date until 30 days post index date. (ICD-9: xx-199.xx; ICD-10: C77-C79, except ICD9: 198.0 Secondary malignant neoplasm of the kidney and ICD10: C79.0 Secondary malignant neoplasm of the kidney and renal pelvis).
 - CCI [REDACTED]
- Continuous enrollment from 12 months prior to the index date. Patients will be required to have continuous enrollment from their index date until the end of the available data. This will allow for sub-analysis of cohorts with 3 months, 6 months and 12 months of available data.

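### Table 6 defines lung metastasis by the whole ICD-9 family 197.0x but by the single ICD-10 code C78.00, so lung may be under-counted at baseline and Other over-counted

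*Combined protocol and SAP*

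**What the plan says.** Section 6.3.2, Table 6, reports location of metastasis as the percentage of patients with each site. The lung row reads "Lung (ICD9-197.0x, ICD10-C78.00". The residual row reads "Other (ICD9 196.xx-199.xx and ICD10 C77-C80 exclusive of above categories".

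Two other rows are printed without the leading letter: "Bones (ICD9-198.5x, ICD10-79.5x" and "Adrenal gland (ICD9-198.7x, ICD10-79.7". The lymph node, lung, liver and brain rows all carry it, for example "Liver (ICD9-197.7x, ICD10-C78.7".

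Entry to the study (Section 6.2.1) uses the full C77-C79 range. The only exception on the ICD-10 side is "ICD10: C79.0 Secondary malignant neoplasm of the kidney and renal pelvis". The same section lists the primary kidney codes as "ICD-10: C64.1, C64.2, C64.9".

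Section 6.1 (Analysis 2) names site of secondary malignancy, over the six months before index, among the baseline characteristics of the first-line cohorts. Section 6.7 says that no separate SAP is needed. Section 6.8 says that programming follows the protocol's specifications. Table 6 is therefore the working definition.

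**The concern.** The two halves of the lung row differ in breadth. The ICD-9 half takes a family and the ICD-10 half takes one terminal code. Elsewhere the protocol writes an x when it means a family, as in 198.5x in this table and K70.4x in the hepatic impairment row. C78.7 or C77 could be read as a parent code that brings its children with it. C78.00 cannot, because a prefix match on it returns only itself.

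The error would be silent. C78.00 is a well-formed code, the program would run, and the lung row would fill with some patients. A second programmer working from the same list would reproduce the result. Section 6.4 plans replication across databases to validate results, but a shared code list carries the same restriction into each, so agreement between databases would not be a check on it.

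At stake is a descriptive baseline percentage for each first-line cohort, and the standardized difference that Section 6.7 plans for each variable.

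**Working it through.** The plan states no figure on this point, so there is nothing to reproduce. The check applies the printed rules to test codes and then bounds the effect.

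**Inputs.** The site rows and residual row come from Table 6. The kidney codes and entry range come from Section 6.2.1. Codes such as C78.01 and C78.02 are not in the protocol. They are assumed, for two reasons:
- C78.00 has two digits after the point, which suggests siblings.
- The kidney entry already spreads one organ over three codes.

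**Rule.** Match by prefix, treat x as a wildcard, and send any unmatched code from C77 to C80 to Other.

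| Test code | As printed | Letter C restored | C restored and lung set to C78.0x |
|---|---|---|---|
| C78.00 | Lung | Lung | Lung |
| C78.01, C78.02 | Other | Other | Lung |
| C79.51, C79.52 | Other | Bones | Bones |
| C79.70, C79.71, C79.72 | Other | Adrenal | Adrenal |
| C77.2 | Lymph nodes | Lymph nodes | Lymph nodes |
| C78.7 | Liver | Liver | Liver |
| C79.31 | Brain | Brain | Brain |

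Restoring the letter C repairs bone and adrenal but leaves lung unchanged. Only the wildcard repairs lung. The brain row has the same shape (198.3x against C79.31). The protocol does not say whether that is deliberate, and nothing here rests on it.

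**Bound.** Take the bone and adrenal rows as corrected.
- N = patients with any look-back claim in 197.0x or the C78.0 family.
- K = those of N with at least one claim that the lung row catches as printed.
- R = those of N − K who already hold another code that falls in Other.

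Then:
- Lung shortfall = N − K.
- Rise in Other = N − K − R, which is at most N − K.

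The protocol gives none of N, K or R, so neither quantity can be evaluated.

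**Could the ICD-9 half rescue the row?** Index treatment must be "recorded in the database between April 2018-March 31, 2019, among those with no aRCC treatment in their history". Six months before April 2018 is October 2017, so the look-back runs from then at the earliest. I assume that claims of that period are mainly in ICD-10. The protocol does not settle this; Section 6.4 describes diagnoses in the Optum claims as ICD-9-CM. Where claims are in ICD-9, the lung row is complete and the problem does not arise.

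**Does it reach the cohort?** No. An unlisted C78.0 code lies inside C77-C79 and counts towards entry.

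**The case against.** The strongest reply is that the lung problem depends on codes that the protocol never lists. That stands as a limit: the text proves the asymmetry, while the misclassification is conditional on the C78.0 family having other members.

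Second, 79.5x and 79.7 are plainly typing slips. The entries are labelled ICD-10, four other rows carry the C, and only one reading makes sense. A reader might infer that bone and adrenal metastases will vanish from the tables. That would happen only under literal programming. A programmer would probably correct it, and an almost empty bone row should be conspicuous at the independent review in Section 6.8. A partly filled lung row would not stand out in the same way.

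Third, one C78.00 claim keeps a patient in Lung, and entry requires at least two secondary-malignancy codes 30 or more days apart, so many patients have more than one chance to be caught. This limits the shortfall without removing it: the entry codes may be for any site, and the entry window is longer than the six-month look-back.

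Fourth, the variable is descriptive, and Section 6.7 plans no stratification or adjustment by site. That stands and sets the weight of the point.

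**Conclusion.** The lung entry should be corrected. If the C78.0 family has members other than C78.00, and if look-back claims are mainly in ICD-10, the printed list under-counts lung metastasis. It over-counts Other by no more than the lung shortfall. The restored letter C is clerical.

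Several stronger readings are tempting, and the protocol does not support them:
- **A stated size.** There are no counts by code, so any percentage would only restate an assumption.
- **An equal rise in Other.** A patient can count at several sites, so someone already in Other adds nothing.
- **Damage to selection or outcomes.** Entry uses the full range, and treatment failure, cost, utilization and survival do not use the site variable.
- **Loss of a prognostic factor.** The protocol lists site as a baseline characteristic and does not call it prognostic.
- **A need to cut Other back to C77-C79.** The residual row pairs ICD-9 196-199 with C77-C80, so dropping C80 alone could create a new mismatch.

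**What to change.** In Table 6, change the lung ICD-10 entry from C78.00 to C78.0x, so that it has the same breadth as 197.0x. In the same edit, print the bone entry as C79.5x and the adrenal entry as C79.7x. Leave the range of Other as it is. While the table is open, confirm whether the single code in the brain row is intended.

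The cost is an edit to one code list before programming. No design, eligibility or outcome definition changes. If tables have already been run, only the site rows and their standardized differences need regenerating.
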